Socially Assistive Robots for Interaction With Older Adults With Dementia

NCT04384978

Date: 4/20/2021

Objectives.

The study will evaluate the overall effectiveness of Ryan Companionbot (aka Ryan) with interactive gameplay to have a positive impact on a user's cognitive function, performance of activities of daily living, and mood. An active control group will perform solitary physical and cognitive activities such as walking and crossword puzzles, sudoku, or solitaire. Our hypothesis is individuals playing interactive cognitive and physical games with Ryan will have a greater positive effect on cognitive function, performance of activities of daily living, and mood compared to individuals engaging in solitary physical and cognitive activities.

Design.

The study addresses design and analysis problems common to published brain training intervention studies and follows recommended best practices of preregistration, adequate documentation, pretest baseline, control conditions, sampling and randomization, dosing, blinding, contingent analysis, statistical analysis, and scattershot publishing without full documentation. The pilot study will be comprised of two groups of people diagnosed with mild Alzheimer's disease and related dementia senior subjects. Subjects will play games with and administered by Ryan, 2-3 times a week and 30-minutes per day. The team will measure the changes and improvement in the social/emotional well-being of these two groups and eventual changes in the cognitive/memory functions of elderly people living in a similar environment.

Methods.

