The study with Ryan CompanionBot will occur in ESC's and Kavod's library or atrium or a location free of distractions and intrusion. A staff member will be present during all sessions to assist with user operation, document behavioral observations, and ensure the safety of participants by intervening if the subject shows signs of distress. Ryan's sensors will record all of the subject's activities and interactions including the gameplay. The system will record all dialogs between the subjects and Ryan, along with Ryan's decisions for additional analysis of the individuals' behaviors. Prior to running the sessions, we will interview each participant and his/her caregivers to understand the main weaknesses and problems related to physical and cognitive limitations from their dementia, and to learn about their favorite colors, objects, animals, music, names of close relatives, and cherished belongings to personalize the experience. Participants will complete the Saint Louis University Mental Status (SLUMS) test, a screening method for Alzheimer's and other dementia. Scores range from 0 to 30. Scores of 27 to 30 are considered normal in a person with a high school education. Scores between 21 and 26 suggest a mild neurocognitive disorder. Scores between 0 and 20 indicate dementia. The measurement will be conducted three times throughout the study.

Statistical Analysis Plan.

Statistical analysis will include multi-way Analysis of Variance (ANOVA) to find the significance of the findings and the effect of different parameters and variables on the measured outcomes within and between the two groups.

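### Does the session staff member's double role, with no stated SLUMS assessor, undermine the plan's claim of blinding?

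*Combined protocol and SAP*

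**What the plan says.** Blinding is mentioned once, in the Design section. The study is said to address known problems of brain-training research, and it "follows recommended best practices of preregistration, adequate documentation, pretest baseline, control conditions, sampling and randomization, dosing, blinding". No role (participant, session staff, assessor or analyst) is named as blinded, and no method is described.

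The Objectives define the comparator: "An active control group will perform solitary physical and cognitive activities such as walking and crossword puzzles, sudoku, or solitaire". The hypothesis concerns "cognitive function, performance of activities of daily living, and mood compared to individuals engaging in solitary physical and cognitive activities". The Design adds a further area: "The team will measure the changes and improvement in the social/emotional well-being of these two groups". No instrument is given there.

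The Methods describe three kinds of data collected after the pre-session interview:

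- **Staff notes:** "A staff member will be present during all sessions to assist with user operation, document behavioral observations". The same person also watches over participants' safety.
- **Robot recordings:** the sensors capture the participant's activities and gameplay, and "The system will record all dialogs between the subjects and Ryan". The stated purpose of these system records is supplementary study of how individuals behave.
- **SLUMS**, a 0 to 30 cognitive screen: "The measurement will be conducted three times throughout the study". No assessor is named.

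The Statistical Analysis Plan applies multi-way ANOVA to find "the effect of different parameters and variables on the measured outcomes within and between the two groups". It does not list those outcomes.

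**The concern.** A reader who sees blinding on the list looks for the person who is blinded. The only individual observer described helps deliver the session, so that person knows what the participant is doing. The other rich data source, conversation with the robot, should have no counterpart in a solitary control group. Social and emotional well-being is to be measured in both groups with no named instrument, and the ANOVA covers outcomes that are not listed. It is easy to infer that the notes or recordings would fill the gap.

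If they did, a group difference in behaviour or well-being could reflect what the observer expected to see, or could have no control data behind it. For SLUMS the stake is smaller but real: without a statement about the assessor, a reader cannot judge whether expectation could have influenced the scoring.

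**Working it through.** The documents give no sample size, standard deviation, effect size or error rate, so there is nothing to recompute. The check sets the statements side by side.

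**1. Could the staff notes be a blinded comparison?** The Methods say staff attend all sessions, in a paragraph that opens with the robot sessions. There are two readings.

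| Reading of all sessions | Consequence for the notes |
|---|---|
| Both groups | The observer sees the robot or the crossword and cannot be masked |
| Robot sessions only | There are no control notes to compare |

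On either reading the answer is no.

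**2. Could the dialogs be a blinded comparison?** A dialog with the robot requires the robot. Under the solitary control in the Objectives, such data exist in one group only, so again no. This step is conditional. One Design sentence says, without restriction to a group, that subjects play games with the robot. Read literally, it covers everyone. Read with the Objectives, it describes the intervention schedule, which is the natural sense because the hypothesis contrasts robot play with solitary activity.

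**3. Does the plan use either source that way?** Nothing in the Objectives, Design, Methods or Statistical Analysis Plan names the notes or recordings as a between-group outcome. The notes are linked to no outcome at all. The system records are for supplementary behavioural work. That well-being has no stated instrument shows only that the instrument is unstated. It does not follow that the notes are the instrument.

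**4. Is the blinding claim contradicted?** Open session staff do not contradict it, because blinding can refer to those who score outcomes or analyse data. The list is also a loose one. It ends with piecemeal, poorly documented publication, which is a fault to avoid and not a practice to follow. One word in it is weak evidence of a specific commitment.

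**5. What is left for SLUMS?** It is the only outcome instrument named, and it can be given in the same way to both groups. The text is silent on who scores it. A masked assessor and an open one are both compatible with what is written, so the accurate description is masking not stated, rather than masking absent.

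**6. What would a change alter?**

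- Labelling the notes and recordings as descriptive rules out an analysis the plan does not describe, so no stated result moves.
- Describing blinding by role, with either a masked or an open SLUMS assessor acceptable, leaves the conduct of the trial as it is.
- Tidying the Design sentence confirms the reading that the Objectives already support.

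**The case for a change.** The best case for acting is that the Statistical Analysis Plan defines no outcomes, so nothing formally keeps the notes or recordings out of the ANOVA. The plan also tests a directional hypothesis between groups and presents itself as following best practice, so calling it a pilot is not a full excuse. A by-role statement would cost a few sentences and would protect readers from a misleading claim.

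Parts of this stand. Steps 1 and 2 are sound: these two sources cannot support a blinded comparison while the control is solitary. The SLUMS assessor really is unstated, and a careful author would have named the role.

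It does not carry the point further, for two reasons. First, the harm depends on a use of the notes or recordings that has to be supplied by the reader. Second, confining the ANOVA to measures taken alike in both groups is not free on the present text. SLUMS is the only such measure named, so activities of daily living and mood, two of the three outcomes in the hypothesis, would be left with no between-group test. The absence of instruments for those outcomes is a separate question from blinding and should not lend weight to this one. The same is true of the unstated schedule and staffing of control sessions.

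**Conclusion.** No change to the plan follows. The wording on blinding is thin and the SLUMS assessor is not identified, but these are omissions of detail that the investigators can fill sensibly in procedures and in the report. They do not show a faulty design or an analysis that would give a wrong answer. Session staff who know the activity are inherent in this comparison, and their presence also serves safety.

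No bias is quantified, and the documents offer no basis for doing so.

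The conclusion rests on three assumptions: the control group is solitary, as the Objectives say; the notes and recordings stay descriptive; and the report states who scored SLUMS and whether that person knew the group. If the notes or dialogs were later presented as a blinded group comparison, the criticism would apply in full to that result. If SLUMS was scored openly, a group difference should be read with that in mind.

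### The SAP's open multi-way ANOVA does not fix which group effect tests the hypothesis; one baseline-adjusted SLUMS contrast should be named, once the three assessment times are stated

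*Combined protocol and SAP*

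**What the plan says.** The Statistical Analysis Plan section consists of one sentence. It begins "Statistical analysis will include multi-way Analysis of Variance (ANOVA) to find the significance of the findings" and goes on to the effect of unspecified variables "on the measured outcomes within and between the two groups". It lists no factors, within-person term, error term, covariate, time point, contrast or alpha.

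Four other statements bear on the point:

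- **Methods, instrument.** "Participants will complete the Saint Louis University Mental Status (SLUMS) test"; the section ends with "The measurement will be conducted three times throughout the study". No dates are attached to the three assessments. SLUMS is the only outcome instrument named.
- **Methods, timing.** "Prior to running the sessions, we will interview each participant and his/her caregivers" dates the interview. The SLUMS sentence that follows has no such time marker, so it is an assumption that the first SLUMS is a pretest.
- **Design.** The practices said to be followed include "pretest baseline, control conditions, sampling and randomization". How the baseline enters the analysis is not stated.
- **Objectives.** The hypothesis is a between-group one: the robot group does better than the active control on cognition, daily activities and mood.

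**The concern.** The hypothesis is a difference between two groups. The plan names a family of analyses and does not say which member tests it. Three scores per person are correlated, and a baseline can be handled in several ways: as a level of the time factor, as something subtracted, or as a covariate. Each choice answers a somewhat different question with different precision.

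On the natural reading, a group-by-time repeated-measures ANOVA, two effects involve group:

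- **Group main effect.** This compares the groups on the average of all three visits. If the first visit is a pretest, no treatment effect can exist there, so the average is pulled towards zero.
- **Group-by-time effect.** This does address change, but as a two-degree-of-freedom test. It gives no single estimate in SLUMS points, and on its own it does not show which group did better.

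If the choice between them is left until the data are seen, it can decide the answer. A baseline-adjusted contrast fixed in advance removes the choice and uses the pretest to gain precision.

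**Working it through.** **Inputs.** From the documents: two groups, three SLUMS assessments, ANOVA as the only named method, and a pretest baseline in the list of practices. The plan has no sample-size or power figure to reproduce. Everything else is assumed: two-sided 5% tests, n = 20 per arm, complete data, SD of 1 at each visit, and equal correlation r between visits with r = 0.5, 0.7, 0.8 or 0.9. Effects at visits 1/2/3, in SD, are rising (0/0.3/0.6), sustained (0/0.6/0.6) or waning (0/0.6/0.3).

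**Formulas, worked for the rising effect at r = 0.7**

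1. Group main effect. Mean effect m = 0.3; variance of a person's three-visit mean = (1+2r)/3 = 0.8. Noncentrality = m / √[(2/n)(1+2r)/3] = 0.3/√(0.1 × 0.8) = 1.061, on 38 df. Power 17.9%.
2. Group-by-time. λ = (n/2)·Σd²/(1−r), where d is each visit's effect minus the mean effect: −0.3, 0, 0.3, so Σd² = 0.18. λ = 10 × 0.18/0.3 = 6.0, F on 2 and 76 df. Power 56.6%.
3. Change score at the final visit. Variance 2(1−r) = 0.6. Noncentrality = 0.6/√(0.1 × 0.6) = 2.449, on 38 df. Power 66.5%.
4. Baseline-adjusted final visit. Variance 1−r² = 0.51. Noncentrality = 0.6/√(0.1 × 0.51) = 2.657, on 37 df. Power 73.5%.

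**Power (%) at r = 0.5 / 0.7 / 0.8 / 0.9**

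| Test | Rising | Sustained | Waning |
|---|---|---|---|
| Group main effect | 20.5 / 17.9 / 16.8 / 16.0 | 32.7 / 28.1 / 26.3 / 24.8 | 20.5 / 17.9 / 16.8 / 16.0 |
| Group-by-time | 36.5 / 56.6 / 75.3 / 96.9 | 47.0 / 69.9 / 87.0 / 99.4 | 36.5 / 56.6 / 75.3 / 96.9 |
| Change score, final visit | 45.6 / 66.5 / 83.2 / 98.5 | 45.6 / 66.5 / 83.2 / 98.5 | 15.2 / 22.3 / 31.0 / 54.3 |
| Baseline-adjusted, final visit | 56.9 / 73.5 / 86.8 / 98.9 | 56.9 / 73.5 / 86.8 / 98.9 | 18.7 / 25.3 / 33.8 / 56.3 |

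**Check on the proposed model.** The two-visit mixed model was simulated directly (40,000 trials per setting, with 2n−3 df standing in for Kenward-Roger). For the rising effect at 20 per arm, power was 56.2 / 73.0 / 86.3 / 98.8%, close to the closed form. Size was 4.9-5.2% for 10, 20 and 30 per arm.

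**Range over sample size, rising effect.** With 10 per arm the group main effect has 10-12% power against 30-82% for the proposed model; with 30 per arm, 22-29% against 75-100%.

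**Gain over a change score.** The variance ratio is (1−r²)/[2(1−r)] = (1+r)/2 = 75 / 85 / 90 / 95%. The gain is material at r = 0.5-0.7 and small at 0.8-0.9.

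**If either group effect were counted as positive.** 1 − 0.95² = 9.75% false positives. Simulation (20,000 trials per setting; 10, 20 and 30 per arm) gave 9.3-10.0%.

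**The case against.** **The remedy is partly a preference.** A group-by-time test fixed in advance would also close the gap. With a sustained effect it matches baseline adjustment from about r = 0.7-0.8 (69.9% against 73.5%, then 87.0% against 86.8%). With a waning effect it is clearly better: 37-97% against 19-56%. This stands. The case for the baseline-adjusted contrast is one interpretable estimate and usually better precision, not superiority under every pattern.

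**The final visit is undefined.** The third SLUMS could fall at the end of the intervention or at a later follow-up, where it would measure persistence. This also stands. The visits must be dated before any contrast is chosen.

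**The group main effect may never have been the intended test.** "The team will measure the changes and improvement in the social/emotional well-being of these two groups" points towards change over time, and the Design calls the study a pilot. This makes reliance on the main effect less likely, but it does not name a test, and the SAP still plans significance testing.

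**Stronger readings.** A reader might infer that the three scores will be analysed as if they came from different people, or that ANOVA is the wrong method. The documents support neither. The SAP refers to effects within as well as between groups, which suits a repeated-measures analysis. Such an analysis is sound with complete data and sphericity or a correction. The condition matters: with unequal correlations of 0.8/0.5/0.8, the uncorrected test had a simulated size of 6.7% at 20 per arm. A reader might also take 9.75% as the trial's false-positive rate. The plan states no rule that either effect counts, so the figure is conditional on such a rule.

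**Conclusion.** The concern holds in a limited form. The SAP does not date the three SLUMS assessments, list the model terms, say how the baseline enters, or name the effect that tests the between-group hypothesis. On the favourable reading the analysis is valid but leaves two group tests open, and one of them is diluted by the pretest visit.

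The size depends on the pattern of effect. At 20 per arm with a rising effect, power is 16-21%, 37-97% or 57-99% according to which effect is read. The loss from using the group main effect is smaller when the effect is sustained and r = 0.5 (33% against 57%), so it would be wrong to say that most of the power is always lost.

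These figures rest on assumed sample size, correlation, effects and alpha, and on the first SLUMS being a pretest. They show that the open choice matters; they are not estimates for this trial. The SAP sentence is also not tied to SLUMS alone and says only what the analysis will include, so the finding is that no deciding contrast is fixed, not that a wrong one has been.

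**What to change.** 1. State when each of the three SLUMS assessments takes place, confirm that the first precedes the sessions, and identify which one marks the end of the intervention.
2. Before outcome data are seen by group, replace the open ANOVA for SLUMS with one mixed model of the two post-baseline scores: group, visit, group-by-visit and baseline SLUMS, with unstructured within-person covariance and Kenward-Roger degrees of freedom.
3. Fix one between-group contrast from that model as the single SLUMS result, in SLUMS points with a 95% CI. By default, take the adjusted difference at the end-of-intervention assessment.
4. State who is included (for example, everyone randomised with a baseline and at least one later SLUMS) and report by group how many are not.
5. Label all other ANOVA effects exploratory. Use the same form for daily activities and mood where a baseline exists. Multiplicity across the three domains is a separate decision.

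**Cost.** SAP wording and one degree of freedom for the baseline; no new data if the first SLUMS is already a pretest. The downside is lower power than group-by-time if the effect has waned by the chosen visit, which is why the visits must be dated first.

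### The named ANOVA, with no rule on testing or analysing participants who stop sessions, leaves the three-visit SLUMS comparison open to bias in either direction

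*Combined protocol and SAP*

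**What the plan says.** The Statistical Analysis Plan is one sentence. It names "multi-way Analysis of Variance (ANOVA) to find the significance of the findings" and applies it to "the measured outcomes within and between the two groups". It gives no factors, error structure, analysis set or missing-data rule.

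Methods introduces SLUMS ("Scores range from 0 to 30", higher being better) and adds: "The measurement will be conducted three times throughout the study". It gives no dates, and does not say whether the later tests depend on continued attendance.

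Methods also has a staff member present at the Ryan sessions to "ensure the safety of participants by intervening if the subject shows signs of distress". Nothing comparable is described for the control condition, which Objectives sets out as follows: "An active control group will perform solitary physical and cognitive activities such as walking and crossword puzzles, sudoku, or solitaire".

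The hypothesis in Objectives is directional: Ryan "will have a greater positive effect on cognitive function, performance of activities of daily living, and mood".

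**The concern.** Participants have mild dementia, and some may stop before the third SLUMS. The two activities are very different (a talking, recording robot against solitary walking, puzzles or cards), so equal stopping in the two groups cannot be taken for granted.

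Both natural readings of the named method handle a missing score badly:

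- **Repeated-measures ANOVA.** This is the usual choice for three scores per person with a within-group effect. It needs all three, so a person with one or two is left out and the scores already collected are lost.
- **Long-format multi-way ANOVA.** This keeps the available rows but treats a person's visits as independent observations, so its standard errors are wrong.

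Under the first reading, the people compared are those who finished, not those assigned. If decliners leave one group more than the other, that group's remaining members look better than the group as assigned, and a difference can appear, or a real one can be hidden, without any effect of the activity. Scores that were never collected cannot be recovered at the analysis stage.

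**Working it through.** The documents give no sample size, alpha, standard deviation, dropout rate or follow-up length, so there is no plan figure to reproduce. Three visits, two groups and the 0 to 30 scale come from the documents. Everything else below is an assumption.

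**1. Analytic size, no true effect.** Let d be the fraction of a group that stops (those lowest on a stopping score), ρ the correlation of that score with SLUMS change, SD the standard deviation of change, φ the standard normal density and z_d its d-quantile. The completers' mean change is too high by

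shift(d) = SD × ρ × φ(z_d) / (1 − d),

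and the bias is shift(Ryan) − shift(control).

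- d = 30%: φ(z_d)/(1 − d) = 0.348/0.70 = 0.497
- d = 10%: 0.1755/0.90 = 0.195
- Difference for 30% versus 10%: 0.302

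| Stopping, Ryan vs control | SD 2, ρ 0.3 | SD 4, ρ 0.8 |
|---|---|---|
| 30% vs 10% | 2 × 0.3 × 0.302 = +0.18 | 4 × 0.8 × 0.302 = +0.97 |
| 30% vs 0% | 2 × 0.3 × 0.497 = +0.30 | 4 × 0.8 × 0.497 = +1.59 |
| 20% vs 20% | 0 | 0 |
| 10% vs 30% | −0.18 | −0.97 |

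Positive values favour Ryan.

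**2. Check under a different mechanism.** Take SLUMS SD 4, adjacent-visit correlation 0.7, control complete, and the worst 20% of the Ryan group on baseline-adjusted second score lost. Here φ(z_d)/(1 − d) = 0.280/0.80 = 0.35, and the bias is 4 × 0.7 × √(1 − 0.49) × 0.35 = 0.70 points. A large simulation of this case, with correlations 0.6 to 0.8, gave 0.67 to 0.69.

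**3. Simulation at plausible pilot size.** 3,000 trials per case, no true effect, 30 per group, SD of change about 3.3, ρ = 0.6, nominal two-sided 5%. Stopping before visit 3 depends either on the observed change to visit 2 or on the change to visit 3, which is unobserved for those who stop. The likelihood-type analysis predicts the third score from the first two within each group.

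| Ryan vs control stopping | Depends on | Completers: bias | Completers: type I | Likelihood: bias | SLUMS on everyone: bias | SLUMS on everyone: type I |
|---|---|---|---|---|---|---|
| 30% vs 10% | observed | +0.39 | 7.9% | +0.01 | +0.01 | 5.2% |
| 30% vs 10% | unobserved | +0.60 | 10.1% | +0.38 | 0.00 | 5.5% |
| 10% vs 30% | observed | −0.38 | 8.7% | 0.00 | 0.00 | 5.9% |
| 10% vs 30% | unobserved | −0.60 | 10.2% | −0.39 | 0.00 | 5.0% |
| 20% vs 20% | observed | −0.02 | 5.7% | −0.02 | −0.01 | 5.6% |
| 20% vs 20% | unobserved | −0.02 | 5.3% | −0.01 | 0.00 | 4.7% |

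The standard error of the group difference is 3.3 × √(2/30) = 0.85, so simulation error in a mean bias is about 0.85/√3000 = 0.016. The formula in step 1 gives 3.3 × 0.6 × 0.302 = 0.60 for the second row, as simulated. With no stopping, the ANOVA rejected in 4.8% to 5.9% of trials across 15, 30 and 60 per group. At 60 per group, 30% versus 10% gave a type I error of 10.9% (observed) and 16.5% (unobserved).

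**4. Reading.** The bias changes sign with the imbalance and vanishes when rates and mechanism are equal. A likelihood analysis removes it when stopping is explained by scores already seen; otherwise about 0.4 of the 0.6 points remains. Testing everyone removes it in both cases.

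**The case against.** The strongest objection is that the plan is silent rather than wrong. Four stronger readings are tempting, and the documents support none of them.

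- **That the plan deletes people who stop.** It does not say so. The wording is "Statistical analysis will include multi-way Analysis of Variance (ANOVA) to find the significance of the findings", which does not say repeated-measures or completers-only and need not be exhaustive. Deletion is the likely default, not a stated rule. The alternative reading fails for a different reason, so the sentence needs changing either way.
- **That SLUMS ends when sessions end.** The text neither requires nor rules out later testing.
- **That intervening for distress means withdrawal.** The sentence concerns staff conduct during a session. It mentions neither leaving the study nor missing a SLUMS.
- **That unequal stopping would make Ryan look effective.** That needs more decliners to stop in the Ryan group. The documents do not say which group would lose more, and the reverse pattern works against Ryan.

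It is also fair to say that in a pilot of 30 per group, a bias of 0.4 to 0.6 points is smaller than the standard error of 0.85. That stands as a statement about size. But the bias does not shrink as numbers grow, a confidence interval does not show it, and this plan intends significance tests of a comparative claim.

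**Conclusion.** The point holds as a gap joined to an unsuitable method. The named ANOVA copes poorly with a missing SLUMS under either reading, and nothing keeps participants who stop under assessment or in their assigned group. If stopping is related to decline and differs between groups, the completers-only comparison could be biased in either direction, including towards Ryan.

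Neither sign nor size can be settled from the documents. The range of roughly 0.2 to 1.0 points towards the group losing more decliners rests on assumed stopping of 30% versus 10%, SD of change 2 to 4 and ρ 0.3 to 0.8. At an assumed 30 per group, type I error is about 8% to 10% instead of 5%. If stopping is equal and arises the same way in both groups, the bias largely cancels and the loss is mainly precision. The change should be made before data collection ends; confidence in how much it matters here is medium.

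**What to change.** 1. **Methods.** Replace the sentence on the number of measurements with: *SLUMS is given at three time points fixed from assignment [dates and windows to be stated], to every participant, including those who have stopped sessions, unless they or their representative decline further assessment.* This leaves untouched when sessions are stopped.
2. **Statistical Analysis Plan.** For SLUMS, replace the ANOVA with: *A likelihood-based mixed model for repeated measures, with small-sample degrees of freedom, includes all participants in their assigned group and every SLUMS collected, and gives the group contrast at the last visit.*
3. **Reporting and sensitivity.** Tabulate stops by group and reason. Add a sensitivity analysis that shifts missing final scores over a stated range in each group separately. It should cover both groups because the direction is not known, and it is needed because the model alone does not remove bias when stopping depends on unobserved decline.

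The three SLUMS tests are already planned, so no new instrument is needed. The cost is modest follow-up effort for people who stop, one extra table and one extra analysis. Of the three items, continued testing matters most, since it is the only one that cannot be added after the data are in.
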